2.1 Nonclinical and Clinical Data To Date

The use of solriamfetol to treat EDS has been evaluated and extensively profiled in the literature. Given the shared EDS phenotype between narcolepsy, OSA, and insomnia, such data support that solriamfetol may be useful in those patients who cannot or do not tolerate the iatrogenic effects of sleepiness in CBT-I. Three such studies are listed below:

Krystal, A. D., Benca, R. M., Rosenberg, R., Schweitzer, P. K., Malhotra, A., Babson, K., ... & Strohl, K. P. (2022). Solriamfetol treatment of excessive daytime sleepiness in participants with narcolepsy or obstructive sleep apnea with a history of depression. *Journal of psychiatric research*, 155, 202-210.

Servid, S. (2012). New Drug Evaluation: solriamfetol tablets, oral.

2.2 Human Pharmacokinetics The time to peak levels of solriamfetol is about 2 hours (range 1.25–3.0 hours). Solriamfetol is minimally metabolized in humans. Its elimination half-life is about 7.1 hours.

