3.2 Secondary Objectives (if applicable)

Assess the effects of solriamfetol on daytime sleepiness, fatigue, adherence with “sleep rescheduling”, and on daytime performance

4. Investigational Plan

All subjects will be monitored for 2 weeks prior to treatment, for 8 weeks during treatment, and for 2 weeks following treatment. Additionally, subjects will complete two questionnaires complete two questionnaires (Insomnia Severity Index [ISI] and Retrospective Sleep Continuity Assessment Questionnaire [RSCAQ]) 3 months after completing treatment.3 months after completing treatment. Subjects receiving solriamfetol will take medication at 2pm daily for 4 weeks. Medication use will also include a 1-week placebo run-in and a 3-week placebo “run-out” (8 weeks’ total). Note: This design was used for our prior trials of CBT-I with wake promoting medications. Subjects receiving CBT-I will have 8 weekly

sessions (up to 90 minutes in duration). Daily sleep diaries will be administered to assess for differences in sleep continuity between conditions and over time. Self-report weekly assessments will also be administered and will include standard retrospective measures of insomnia (ISI), sleepiness (Epworth Sleepiness Scale, ESS), depression (PHQ-9), fatigue (Functional Assessment of Chronic Illness Therapy – Fatigue Scale [*FACIT-Fatigue*]), PROMIS-Short Form 7a, and Brief Fatigue Inventory [BFI]), treatment acceptability (MITAS)), and daytime function (Functional Outcomes of Sleep-10 item, FOSQ-10). Daytime function will also be objectively assessed daily via Ecological Momentary Assessment and at the end of baseline treatment, and post treatment periods using a PVT phone-based app. Self-report assessments will be accomplished on-line via RedCap software and subjects will also be asked to complete weekly and monthly questionnaires via Hypknowledge (a PHT Penn Health Tech Clinical Research Tool) site.

Treatment Regimen (as noted above)

The first five participants will be enrolled slowly to observe whether any adverse responses occur (e.g., taking longer to fall asleep after medication administration at 2pm) that would necessitate protocol modifications, for instance to the timing of medication dosing, if not amount.

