Medication: Solriamfetol (SRFTL) or placebo (PLA) will be administered at 2pm daily for 4 weeks. Dosage will (for all subjects) start at 75mg. This dosage was chosen through weighing up the need to extend wake/delay bedtime to consolidate sleep and improve sleep continuity (necessitating a later timing of dose than typical), without inadvertently enhancing wake to the point where it extends sleep latency. Rather than downwardly titrate the medication, the timing of dosing will be altered where required (for example, timing advanced to 1pm or 12pm). Changes in dose timing will occur when the study staff (therapist, PI, and medical collaborator) deem it to be optimal (i.e., in response to extended sleep latency). Subjects in the SRFT + CBT-I arm will also be eligible for changes in dose timing if they report being unable to adhere to the prescribed time to bed (PTTB) component of CBT-I. As noted above, medication use will also include a 1-week placebo run-in and a 3-week placebo “run-out” (eight weeks’ total). The timing of the first administration of SRFTL will (for those receiving CBT-I) align with the start of sleep restriction (Session 2).

All study medication will be provided by Axsome Pharmaceuticals (no cost) and will be received, stored, and packaged by the University of Pennsylvania Investigational Drug Service (IDS). DS will create blister packs for each patient that are identical and will allocate active medication and placebo according to treatment condition. This will enable double blinding of the study. All doses will be over-encapsulated, and all daily doses will be delivered as a single capsule. The use of blister packs will also allow us to not only track adherence but to identify the patterning of medication use.

Cognitive Behavioral Therapy: Treatment will be conducted by a master therapist via a HIPAA compliant video link (Zoom), with 1-2 members of our established cohort of CBT-I experts (n=17) serving as backup therapists. Sessions 1-8 will follow our published protocol (published in 2005 by Springer). Each session will be conducted individually and have a singular focus per session. All sessions following the delivery of sleep restriction therapy & stimulus control instructions (post Session 2) will include, as needed, management of non-adherence and/or time-in-bed titration. The Session specific itinerary will be as follows.

Session 1: evaluation and orientation

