"Subjects who withdraw consent to participate in the study will be asked to return their foil packs. Please see section 5g".

f. Early Termination Visits

See section; Subject Withdrawal

g. Subject Contact

Subjects will be contacted through phone, email, and via HIPAA compliant Zoom. Identifying information, such as names, will not be used.

Axsome Study - Table of Instruments						
Instrument Name	Abbreviation	Pre	Daily	Weekly	Post	Follow-up (3 mo.)
Sleep Disorder Symptom Checklist	SDS-CL-25	X			X	
Insomnia Severity Index	ISI	X		X	X	X
Retrospective Sleep Continuity Assessment Questionnaire	RSQAQ					X
Daily Sleep Diary	DSD		X			
Epworth Sleepiness Scale	ESS	X		X	X	
Brief Fatigue Inventory	BFI	X		X	X	
Functional Assessment of Chronic Illness Therapy – Fatigue Scale	FACIT-F	X		X	X	
PROMIS-SF 7a	PROMIS	X		X	X	
Functional Outcomes of Sleep Questionnaire	FOSQ-10	X				X
Profile of Mood State Questionnaire	POMS	X				X
Patient Health Questionnaire	PHQ-9	X		X	X	
Medical Symptom Checklist	MSCL	X		X	X	
Morin Insomnia Treatment Acceptability Scale	MITAS					X
Ecological Momentary Assessment	EMA		X			
Psychomotor Vigilance Test	PVT		X			

9. Study Evaluations, Measurements, and Schedule

a. Medical Record Review N/A

b. Physical Examination N/A. Physician Assent will be ascertained.

c. Vital Signs N/A. Physician Assent will be ascertained.

d. Laboratory Evaluations

The primary lab evaluation at screening is the Home Sleep Apnea Testing (HSAT, type 3 or 4 sleep study).

e. Pregnancy Testing

An effective method of birth control (as determined by their physician and intake) is required for women who are pre-menopausal. There are no requirements regarding the specific form of contraception that must be used. Subjects must agree to continue to use this method of birth control during the entire course of the study. If a subject does become pregnant during the study, they will be disenrolled. Outcome data on incidental pregnancies will not be collected.

f. Other Evaluations, Measures N/A

g. Efficacy Evaluations

The primary efficacy evaluation is accomplished with on-line prospective sampling, e.g., daily sleep diaries and the completion of weekly questionnaires.

h. Pharmacokinetic Evaluation N/A

i. Genetic Testing (only if applicable) N/A

j. Safety Evaluations

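### The PVT has two conflicting schedules: section 4 places no session in the active-drug weeks, and neither schedule sets a test hour

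*Combined protocol and SAP*

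**What the plan says.** The secondary objective (section 3.2) is to "Assess the effects of solriamfetol on daytime sleepiness, fatigue, adherence with “sleep rescheduling”, and on daytime performance". Section 10.n lists the PVT as a daytime-function outcome alongside FOSQ-10 and POMS, both of which are questionnaires.

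The timing of the PVT is given in two places:

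- **Section 4 (Investigational Plan)** contrasts daily Ecological Momentary Assessment (EMA) with a PVT taken "at the end of baseline treatment, and post treatment periods using a PVT phone-based app". A comma seems to be missing after the word baseline; the natural reading is three sessions, one at the end of each period.
- **Section 8.g (Table of Instruments)** has a row for "Psychomotor Vigilance Test" whose only mark is under Daily. Pre, Weekly, Post and Follow-up are empty.

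The periods are defined in section 4: "All subjects will be monitored for 2 weeks prior to treatment, for 8 weeks during treatment, and for 2 weeks following treatment". Within treatment, "Subjects receiving solriamfetol will take medication at 2pm daily for 4 weeks", and "Medication use will also include a 1-week placebo run-in and a 3-week placebo" run-out, for 8 weeks in all. The capsule time is not fixed for every subject, because the regimen allows "timing advanced to 1pm or 12pm".

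No section gives a clock time for the PVT or a time relative to the capsule. The analysis in section 10.n is condition by time, with pre and post as the two levels for the primary outcome. It does not say which PVT week enters.

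**The concern.** The two schedules lead to different data. Staff who follow section 4 collect no PVT while subjects take solriamfetol, and those data cannot be recovered later. Staff who follow the table collect on-drug data, but at whatever hour each subject chooses, and the analysis plan does not say whether those sessions are used.

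At stake is the performance part of the secondary objective. If section 4 is followed and the arms do not differ on the PVT, the report could be taken to say that solriamfetol does not help daytime performance, when performance on the drug was never measured.

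**Working it through.** **Inputs.** Periods of 2, 8 and 2 weeks, and capsules of 1 week placebo, 4 weeks active and 3 weeks placebo (section 4). Time to peak about 2 h and half-life about 7.1 h (section 2.2). Dose at 2 pm, with possible moves to 1 pm or 12 pm (section 4).

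**Step 1: the plan's own figure.** 1 + 4 + 3 = 8 weeks, which agrees with the stated total.

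**Step 2: calendar, with day 1 as the first day of treatment.** Week 1 is days 1 to 7. Active drug lasts 4 × 7 = 28 days, so days 8 to 35. Treatment ends on day 8 × 7 = 56 and the post-treatment period on day 56 + 14 = 70.

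| Schedule | PVT sessions | Sessions in days 8 to 35 |
|---|---|---|
| Section 4 | end of baseline, day 56, day 70 | 0 of 3 |
| Section 8.g, daily | (2 + 8 + 2) × 7 = 84 | 28 of 84 |

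The daily count assumes that the mark covers all three periods, as it must for the sleep diary, which is also marked Daily only.

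**Step 3: gap from the last active dose under section 4.**

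- Day 56: 56 − 35 = 21 days, and 21 × 24 / 7.1 = 71 half-lives.
- Day 70: 70 − 35 = 35 days, and 35 × 24 / 7.1 = 118 half-lives.

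No drug remains at either session.

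**Step 4: what an unset hour means under the daily schedule.** Assume a 2 pm dose, a peak at 2 h and simple exponential decline. The fraction of peak at t hours after the dose is then 2^(−(t − 2)/7.1). A one-compartment model with first-order absorption at steady state, fitted to the same two figures, is shown beside it.

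| Test time | t (h) | Simple decline | One-compartment |
|---|---|---|---|
| 4 pm | 2 | 1.00 | 1.00 |
| 6 pm | 4 | 0.82 | 0.87 |
| 8 am next day | 18 | 0.21 | 0.22 |
| just before next dose | 24 | 0.12 | 0.12 |

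Both models are assumptions. Section 7.e says that over-encapsulation may slow absorption, so the values are indicative. They describe plasma level, not PVT score.

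**Step 5: does a fixed afternoon hour survive a moved dose?** Under the one-compartment model, the fraction of peak is:

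| Dose time | Test at 4 pm | Test at 6 pm |
|---|---|---|
| 2 pm | 1.00 | 0.87 |
| 1 pm | 0.95 | 0.79 |
| 12 pm | 0.87 | 0.72 |

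A window of that kind stays between 0.72 and 1.00 for all three dose times. A test at 2 pm would not: about 0.12 just before a 2 pm dose, against 1.00 after a 12 pm dose.

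**The case against.** Several points on the other side have weight.

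- **The run-out is deliberate.** Section 4 says that the design was used in prior trials, and section 10.k places the primary endpoint at the end of post-treatment. An off-drug PVT fits that frame. This stands: the off-drug contrast is legitimate and should stay. It answers a different question from performance on the drug.
- **A null result is not built in.** A reader might infer that section 4 guarantees no PVT difference. The documents do not support that. The stated mechanism is that wake extension consolidates sleep, and such a benefit could outlast dosing. The half-life counts show only that drug is absent.
- **Treatment could mean the four active weeks.** The study summary gives the duration of administration as 4 weeks. On that reading one of the three sessions is on drug. Section 4, however, defines treatment as 8 weeks, in the paragraph that also schedules the PVT.
- **The table may be unreliable.** It marks FOSQ-10, POMS and MITAS at the 3-month follow-up, where section 5.4 lists only ISI and RSCAQ. But the PVT row carries a single mark, and wherever that mark belongs it cannot stand for three period ends. A conflict remains.
- **The two problems exclude each other.** If the table governs, the on-drug sessions exist and what is left is noise from test time. This is correct. Nor should the exposure ratios be read as lost effect, since no document links plasma level to PVT score.
- **The PVT is not the only measure that the protocol calls objective.** Section 4 uses that word for EMA too, although it describes no performance task there. The supportable statement is that the PVT is the only performance test in the section 10.n list.
- **The stakes are secondary.** The daytime-performance hypothesis in sections 5.6.2 and 10.l is exploratory and does not name the PVT.

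**Conclusion.** The point holds. Section 4 and the Table of Instruments give incompatible PVT schedules, and nothing reconciles them. With treatment as the 8 weeks that section 4 defines, its schedule has 0 of 3 sessions in the active weeks. The later two, 21 and 35 days after the last active dose, can show only a carried-over benefit. The daily schedule would supply 28 on-drug sessions, but at an unset hour and with no PVT week named in section 10.n.

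The zero count rests on the 8-week definition and on reading the section 4 sentence as three period ends. The within-day figures rest on an assumed pharmacokinetic model and serve only to show that test time should be controlled.

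This should be fixed, because the trial otherwise may not answer part of its own secondary objective. It does not touch diary total wake time or the target of 40 completers.

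**What to change.** Reconcile sections 4, 8.g and 10.n as follows.

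1. **One schedule.** Require the PVT at least in the last baseline week, the final active week (week 5), week 8 and the post-treatment period, in all four arms. If daily testing is intended, say so in section 4 and state how the sessions in each of these weeks are summarised.
2. **One test window.** Use the same afternoon clock window in all arms and periods, late enough to follow the capsule; 4 to 6 pm is an example. A window that moved with the capsule would shift clock time unevenly between arms, because the combination arm has an extra reason for dose-time changes.
3. **Recorded times.** Store the app's time stamp and the actual capsule time, and use time since dose in a sensitivity analysis.
4. **Named contrasts.** In section 10.n, make the week-5 minus baseline change the on-drug PVT contrast for solriamfetol. Report it beside the off-drug pre/post contrast, stating which session counts as post.

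The cost is protocol wording, an app reminder, at most one added phone session relative to section 4, and a less flexible test time for subjects. No new instrument or visit is needed, and dosing is unchanged.

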Solriamfetol (trade name Sunosi), is a norepinephrine-dopamine reuptake inhibitor available in 75mg and 150mg tablets for oral administration during the day. Solriamfetol's primary indication is to treat excessive daytime sleepiness (EDS) in patients diagnosed with OSA or Narcolepsy. It binds to the dopamine transporter and the norepinephrine transporter with affinities (K_i) of 14.2 μ M and 3.7 μ M, respectively), does not undergo significant metabolism in humans, and has a T_{max} of ~2 hours (range 1.25–3.0 hours) and a $T_{1/2}$ of ~7.1 hours. The pharmacokinetic profile of solriamfetol, along with the absence of active metabolites, makes it unlikely that there are accumulation effects with multiple doses over days. See the attachment for a copy of the package insert for solriamfetol.

Solriamfetol will be provided by Axsome Pharmaceuticals (no cost), and managed by, the Investigational Drug Services of the University of Pennsylvania. An over encapsulation technique will be used to ensure that the drug doses and placebo formulations appear identical. The first five participants will be enrolled slowly to observe whether any adverse responses occur (e.g., taking longer to fall asleep after medication administration at 2pm) that would necessitate protocol modifications, for instance to the timing of medication dosing, if not amount.

Solriamfetol or placebo will be administered at 2pm daily for 4 weeks. Dosage will (for all subjects) start at 75mg. This dosage was chosen through weighing up the need to extend wake/delay bedtime to consolidate sleep and improve sleep continuity (necessitating a later timing of dose than typical), without inadvertently enhancing wake to the point where it extends sleep latency. Rather than downwardly titrate the medication, the timing of dosing will be altered where required (for example, timing advanced to 1pm or 12pm). Changes in dose timing will occur when the study staff (therapist, PI, and medical collaborator) deem it to be optimal (i.e., in response to extended sleep latency). Subjects in the SRFT + CBT-I arm will also be eligible for changes in dose timing if they report being unable to adhere to the prescribed time to bed (PTTB) component of CBT-I. As noted above, medication use will also include a 1-week placebo run-in and a 3-week placebo "run-out" (eight weeks' total). The timing of the first administration of SRFTL will (for those receiving CBT-I) align with the start of sleep restriction (Session 2).

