Session 2: data acquisition and delivery of sleep restriction therapy & stimulus control instructions

Session 3: review of sleep hygiene

Session 4: management of non-adherence and/or time-in-bed titration only

Session 5: cognitive therapy [de-catastrophization]

Session 6: management of non-adherence and/or time-in-bed titration only

Session 7: management of non-adherence and/or time-in-bed titration only

Session 8: review of treatment progress and relapse prevention.

All treatment will be delivered by a single master therapist ([name] PhD CBSM). [name] has more than 27 years’ experience with CBT-I, he is one of the authors of our published treatment manual (1), and he is also a co-author of a second CBT-I treatment manual (2). He was a consultant for the VA’s rollout of CBT-I, he jointly conducts the Penn 3-day Basic and Advanced CBT-I courses, and he regularly conducts on-site one-day CBT-I workshops. As a final testament to his expertise, he was one of the first individuals to be certified in behavioral sleep medicine and one of the first to receive the SBSM’s Distinguished Career Achievement Award.

5. General Design

A double blind 2x2 mixed model design. The two factors will be 1) treatment (+/- solriamfetol and +/- CBT-I) and 2) Time (pre-post assessment, with additional follow-up data). Patients with insomnia will be randomly assigned to treatment condition.

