5.6.2 Secondary Study Endpoints

1. Patients treated with CBT-I will have significantly greater improvements in sleep continuity from baseline to post-treatment compared to patients not administered CBT-I.
2. Patients treated with CBT-I in combination with solriamfetol will have significantly greater improvements in sleep continuity from baseline to post-treatment compared to patients treated with CBT-I alone.
3. **Exploratory hypotheses:** Patients treated with CBT-I in combination with solriamfetol will have significantly greater adherence with sleep restriction (i.e., sleep rescheduling, prescribed time to bed [PTTB]) and on daytime performance measures (e.g., ESS, FSS, etc.) compared to CBT-I alone.

i. Primary Safety Endpoints [if applicable]

As noted above, side effects will be assessed in several ways: daily assessments via the sleep diaries, weekly evaluation with a medical symptom checklist (52 symptoms where positive endorsements allow subjects to rate their average severity and number of days affected).

6. Study Population and Duration of Participation

Subjects 25 to 65 years old (inclusive) and who have a stable sleep/wake schedule (no shift work) with a preferred sleep phase between 10:00 PM and 8:00 AM. The recruitment sample will be populated by 40 completed subjects. The study duration will be 12 weeks, with a one-time follow-up at 3 months post-treatment.

a. Inclusion Criteria

Participants will meet the diagnostic criteria for Insomnia Disorder according to Diagnostic and Statistical Manual of Mental Disorders (DSM-5). The complaint of disturbed sleep will meet the following criteria:

- ≥ 30 minutes to fall asleep (SL) and/or ≥ 2 awakenings per night of ≥ 15 minutes duration and/or wake after sleep onset (WASO) time of ≥ 30 minutes where total sleep time (TST) did not exceed 6 hours (unless sleep efficiency [SE] is $\leq 80\%$).
- The problem is present for ≥ 3 nights per week.
- The problem duration exceeds ≥ 6 months.
- The complaint of impaired daytime function must include, although not limited to, the report of daytime fatigue, sleepiness, or both.

Additional inclusion criteria are as follows.

1. Aged 25 to 65 years (inclusive).
2. Have a preferred regular sleep phase between 10:00 PM and 8:00 AM.

b. Exclusion Criteria

Please note that all subjects will have to receive physician assent before being enrolled into the study.

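### The dose-timing change for missed prescribed bedtimes is offered only to the SRFT + CBT-I arm, which blinded staff cannot identify; the eligibility phrase needs correcting (minor)

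*Combined protocol and SAP*

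**What the plan says.** One dosing paragraph appears in Section 2 (description of the product), Section 2.5 (Dose Rationale) and Section 4 (Investigational Plan, Medication). It gives two reasons for moving the dose to an earlier hour.

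- **Sleep latency.** Timing may change "in response to extended sleep latency". No arm is named, so this trigger is not at issue.
- **Prescribed time to bed (PTTB).** "Subjects in the SRFT + CBT-I arm will also be eligible for changes in dose timing if they report being unable to adhere" to the PTTB component of CBT-I. The same eligibility phrase, "Subjects in the SRFT + CBT-I arm will also be eligible for changes in dose timing", stands in all three places.

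The deciders are named: "Changes in dose timing will occur when the study staff (therapist, PI, and medical collaborator) deem it to be optimal".

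Section 5 describes "A double blind 2x2 mixed model design". Under Sections 7.e and 7.f, IDS prepares identical packs, allocates drug or placebo, and carries out the blinding. Section 5.5 gives randomisation to the study statistician and/or IDS staff. The only unblinding route described, in Section 11.u, follows a serious adverse event.

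**The concern.** A rule that names a drug arm can be followed only by someone who knows who is in it. In this trial the people who decide on dose timing are not given that information.

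The arm left out is in the same practical position as the arm named. CBT-I + placebo subjects take a capsule at the same hour and have a prescribed bedtime to keep. If they report the same difficulty, the text offers them no timing change.

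The two arms are compared directly. Secondary hypothesis 2 in Section 5.6.2 reads in part "Patients treated with CBT-I in combination with solriamfetol will have significantly greater improvements in sleep continuity", against CBT-I alone. The exploratory hypothesis compares the same two arms on adherence to PTTB. The outcomes are largely self-reported, through diaries and questionnaires, so blinding matters. Two things would be at stake if the rule were applied literally: the blind for any subject whose timing is changed for this reason, and equal handling of non-adherence in the two CBT-I arms.

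**Working it through.** The rule carries no figure of its own, so the check sets the passages side by side. Arithmetic serves only to bound how many subjects it could concern.

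**1. Who meets the conditions, and whom the rule names**

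| Arm | Has a PTTB | Takes a timed capsule | Named in the PTTB rule |
|---|---|---|---|
| Solriamfetol + CBT-I | yes | yes | yes |
| Placebo + CBT-I | yes | yes | no |
| Solriamfetol, no CBT-I | no | yes | no |
| Placebo, no CBT-I | no | yes | no |

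The PTTB column follows from PTTB being a part of CBT-I (Section 4). The capsule column follows from Section 7.e. Two of the four arms can meet the trigger and the rule names one of them. By design those two differ only in what is in the capsule.

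**2. Whether the deciders can tell the two apart**

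The therapist and PI can know who receives CBT-I. Sections 5, 5.5, 7.e, 7.f and 11.u together put capsule content with IDS and the statistician, and state no exception for the deciders. As worded, the rule cannot be applied by them without learning the allocation.

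**3. What a timing change would reveal on the literal reading**

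- A change with no reason known reveals nothing certain, because the sleep-latency trigger is open to every arm.
- A change known to be for PTTB, seen by someone who knows the rule, marks active drug.
- The absence of a change is not conclusive, because the rule makes a subject eligible and leaves the decision to staff judgement.

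**4. What kind of effect could follow**

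Retiming a placebo capsule has no drug effect, so leaving it where it is withholds no drug benefit. Retiming active drug is part of the regimen under test. The remaining channels are loss of blinding and an expectancy or attention effect of being offered a change. This comes on top of what both CBT-I arms already receive, since sessions after Session 2 "will include, as needed, management of non-adherence and/or time-in-bed titration".

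**5. How many subjects are exposed**

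Arm sizes come from Section 10.m. Its 10 per group reproduces: a one-way ANOVA on four groups with means 0, 15, 15 and 30 minutes, SD 19 and alpha 0.05 has noncentrality 10 × (15² + 15²) / 19² = 4500 / 361 = 12.5 and power 0.811. The middle means are an assumption. Correcting the phrase does not change this figure.

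- Planned completers in the CBT-I arms: 2 × 10 = 20.
- If all 60 recruited are randomised equally, which is not stated: 60 / 4 = 15 per arm, and 2 × 15 = 30. Section 6.e speaks of 40 recruited and completed, which would give 20 again.
- Literal reading: the rule covers 10 to 15 subjects in solriamfetol + CBT-I and 0 in CBT-I + placebo.
- Shorthand reading: it covers all 20 to 30.

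These are arm sizes, not numbers affected. The documents do not give the share of subjects who will report PTTB difficulty, so neither the number retimed nor any bias can be computed.

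**The case against.** The strongest reply is that this is a drafting slip. The same paragraph uses drug language loosely: "Dosage will (for all subjects) start at 75mg" cannot be literally true of placebo subjects. Its closing sentence ties the start of solriamfetol to Session 2 for CBT-I recipients in general, and Section 8 says that every subject gets medication. On this view the arm name stands for any CBT-I subject with a capsule, which is also the only reading that works inside the blind. No unblinding follows, and the remaining risk is uneven application.

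This is quite plausible, but it does not settle the matter. The paragraph does use a general expression for CBT-I recipients elsewhere, while the PTTB sentence names a single arm. If shorthand was meant, the phrase is wrong and staff must guess.

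Two further replies stand in full. No passage lists blinded roles one by one, so the blinding of the deciders is inferred from the double-blind design, the role of IDS and the absence of an exception. Nothing says that subjects are told the rule, so the literal harm depends on who knows both the rule and the reason for a change.

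A reader might also infer that CBT-I + placebo subjects are denied a useful treatment, so that the comparison is biased by the drug itself. The documents do not support that: moving an inert capsule has no drug effect, and moving the active one belongs to the regimen being tested.

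**Conclusion.** The point holds as a wording and operational defect of minor severity. As written, the PTTB trigger cannot be applied by blinded deciders. Taken literally, it puts at risk the blind and the equal handling of two arms compared in secondary hypothesis 2 and the exploratory PTTB-adherence hypothesis, through loss of blinding and an expectancy or attention effect of unknown size. Taken as shorthand, the phrase misstates who is eligible. The documents do not decide between the readings, and the same correction serves both.

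The conclusion rests on the therapist, PI and medical collaborator being blinded to capsule content, which is inferred. Exposure is 20 planned completers, or up to 30 subjects if all 60 are randomised equally.

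Stronger conclusions are not supported. A reader might infer that the blind has been or will be broken; the text shows only that a literal application would require it. A reader might infer that the sponsor chose to treat the arms unequally; loose drafting explains the sentence as well. A reader might carry the concern over to the powered primary hypothesis, because solriamfetol + CBT-I subjects also receive the drug; the documents give no frequency of PTTB-triggered changes from which to size an effect, and none is claimed.

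**What to change.** In Sections 2, 2.5 and 4, replace the words naming the SRFT + CBT-I arm in the PTTB sentence with *All subjects receiving CBT-I, regardless of capsule content*, and have the deciders apply the same blinded criteria in both CBT-I arms. The sleep-latency trigger stays as it is. As optional good practice, log each timing change with its reason (sleep latency or PTTB).

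The cost is one phrase in three places, with no added patients or procedures and no change to the sample size. The downside is that some placebo capsules will be retimed to no effect. In return, a timing change no longer points to active drug.
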